Two such skills-based self-management techniques that may contribute to better pain management and improvements in psychological functioning and sleep quality in Veterans are self-hypnosis (HYP) and mindfulness meditation (MM). Both HYP and MM are easily taught and learned, and therefore could be seamlessly incorporated into clinical practice in VA hospitals and clinics across the country. However, *at this point in time, little is known about the efficacy of HYP and MM interventions for chronic pain in Veteran populations, their effects on co-morbid conditions, and their biological and psychological mechanisms.* Such information is critical to the development of strategies to efficiently and cost-effectively maximize their efficacy and to ensure optimal implementation.

The purpose of this randomized controlled trial is to test the efficacy and mechanisms of HYP and MM on chronic pain in 240 Veterans. Participants will be randomly assigned to 8 group sessions of (1) HYP, (2) MM, or (3) an education control condition (ED). Primary (characteristic pain intensity) and secondary outcomes will be assessed at pre-treatment, three times during treatment, post-treatment, and at 3- and 6-month follow-up. Potential treatment moderators and mediators will also be assessed.

The study will address two aims.

Aim 1: Determine the efficacy of 8 sessions of group delivered HYP and MM training for reducing characteristic pain intensity in Veterans, relative to 8 sessions of ED. The hypothesis associated with Aim 1 is:

Hypothesis 1: *Primary Study Hypothesis.* Veterans receiving 8 sessions of HYP or MM training will report significantly greater pre- to post-treatment decreases in average pain intensity than Veterans receiving 8 sessions of ED.

Aim 2: Evaluate the moderation effects of brain states (as measured by EEG) on response to HYP and MM, relative to ED. The hypothesis associated with Aim 2 is:

Hypothesis 2: *Brain State Moderating Hypothesis (Secondary)*. Pain reduction with HYP and MM will be significantly associated with different patterns of baseline brain activity. Specifically, participants who report the most pain reduction with HYP will evidence higher levels of global theta activity and lower levels of left frontal gamma activity at baseline. Participants who report the most pain reduction with MM will evidence lower levels of alpha activity at baseline. Baseline brain activity will not be significantly associated with pain reduction following ED.

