not testable, but we can look at the variables that were observed in groups with and without missing outcomes data. No association between observed variables and the group (missing vs. no missing) will be considered an indication that the data are missing at random. In addition, we will look at the reported reasons for missing values when available. If we can assume data are missing at random, we will use multiple imputation procedures. If there appear to be non-random missing outcomes data, we will use two methods designed to account for this: Heckman's selection models and pattern-mixture models, both of which model the joint distribution of the outcome and the missing mechanism. In the case of non-ignorable missing data, we will use both methods as a sensitivity analysis. If less than 5% of the data is missing and we can assume ignorable missing data, the following analysis will be performed.

Hypothesis 1 states that Veterans randomly assigned to receive eight group sessions of HYP or MM will report significantly greater pre- to post-treatment decreases in average pain than Veterans receiving eight sessions of ED. The response variable will be change in average pain intensity score from pre- to post-treatment (Pre-treatment score – Post-treatment score). This response variable will be analyzed using an analysis of covariance (ANCOVA) with treatment condition (HYP, MM, ED) as the explanatory variable and the baseline pain as a covariate.

Support for Hypothesis 1 would emerge if a significant treatment main effect is present after adjusting for the baseline covariate, and subsequent post-hoc analyses indicate larger baseline to post-treatment decreases in pain intensity in the HYP and MM conditions, relative to the ED condition. The overall significance level for the test of the null hypothesis that all three treatments have equal effect will be set to 0.05.

Although we anticipate that HYP and MM will have similar effects on the primary outcome variable, these analyses will also allow us to compare the relative effects of HYP and MM with each other, as part of the exploratory aims/analyses.

Pairwise comparisons of the treatment groups will be performed using Tukey method (see for example, Analysis of Messy Data Volume 1: Designed Experiments, Second Edition, by GA Milliken and DE Johnson. 2009, chapter 3).

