Addressing Aim 2 by testing Hypothesis 2. Hypothesis 2 states that baseline EEG activity will predict differential response to HYP and MM, such that those participants who have higher baseline levels of global theta, and lower baseline levels of left frontal gamma will respond to HYP, while participants with lower baseline levels of global alpha will respond to MM. We will test for this moderator using a linear regression analysis, with pre- to post-treatment change in pain intensity as the response (criterion) variable. Treatment Condition, absolute power of baseline theta, alpha, and (left frontal) gamma, and terms representing the interaction between treatment condition and each EEG bandwidth will be the explanatory variables. Significant Treatment Condition X Theta, Alpha, and Gamma interactions, with higher coefficients for baseline theta and lower coefficients for baseline gamma in the HYP group, and lower coefficient for baseline alpha in the MM group would support Hypothesis 2.

Additional exploratory analyses. In addition to testing the two study hypotheses, we propose a series of exploratory analyses (explained below) to take full advantage of the data collected to better understand the effects and potential mechanisms of HYP and MM. However, because these analyses are exploratory, we will report them as such. Any statistically

significant findings will be viewed as providing support for further, more definitive, testing in the future.

Effects of HYP and MM on secondary outcomes. To examine the potential effects of HYP and MM, relative to ED, on co-morbid conditions, we will repeat the ANCOVA analyses planned to test Hypothesis 1 for the secondary outcome variables (assessing pre- to post-treatment decreases in depression, anxiety, sleep disturbance, pain interference, PTSD symptoms) as the response variables, controlling for the respective baseline measures of these secondary outcomes. The response variable will be change in each outcome measure score from pre- to post-treatment (Pre-treatment score – Post-treatment score). This response variable will be analyzed using an analysis of covariance (ANCOVA) with treatment condition (HYP, MM, ED) as the explanatory variable and the corresponding baseline value for each secondary outcome measure as a covariate.

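### The support rule for Hypothesis 2 never tests the EEG slope in the named arm, so a band's condition can be met by a slope in a comparator arm alone

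*Combined protocol and SAP*

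**What the plan says.** Section A2 (repeated in the Précis) states Hypothesis 2 as associations within arms. For self-hypnosis, "participants who report the most pain reduction with HYP will evidence higher levels of global theta activity", together with less left frontal gamma. Those who improve most with MM are expected to have less alpha. For the control arm, "Baseline brain activity will not be significantly associated with pain reduction following ED". The aim itself is worded as moderation: "Evaluate the moderation effects of brain states (as measured by EEG) on response to HYP and MM, relative to ED".

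Section D6x tests this with one linear regression of pre- to post-treatment pain change. The model has main effects for arm and for the three EEG bands (gamma from the left frontal region only), and the plan adds that "terms representing the interaction between treatment condition and each EEG bandwidth will be the explanatory variables". The first requirement for support is "Significant Treatment Condition X Theta, Alpha, and Gamma interactions". The second is an ordering of the arm coefficients, which the plan describes for self-hypnosis as "with higher coefficients for baseline theta and lower coefficients for baseline gamma in the HYP group". For MM the alpha coefficient has to be the lower one.

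The rule includes no test of a coefficient against zero, no named contrast between arms and no check of the ED clause. D6x sets a significance level for Hypothesis 1 ("The overall significance level for the test of the null hypothesis that all three treatments have equal effect will be set to 0.05") but none for Hypothesis 2. D6z bases the sample size on the primary hypothesis only.

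**The concern.** The hypothesis is about the slope of pain reduction on EEG within a named arm. The rule looks at something else: whether the three slopes differ (a 2-df test for each band) and which estimate lies furthest in the stated direction. A slope in ED or MM alone can make the three slopes differ. If it runs opposite to the direction predicted for HYP, the HYP estimate can come out highest while its true value is zero. That band's condition would then be read as showing that theta predicts response to HYP when it does not.

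Aim 2 is one of the trial's two named aims. Section C says that replicated EEG findings would support offering both treatments. That inference should not rest on an untested ordering of estimates.

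**Working it through.** **The plan's own figure.** No power is given for Aim 2. The only power statement is for Aim 1 (D6z): 80 completers per arm, at least 80% power at SD 1. With the least favourable mean decreases (ED 0.3, HYP 0.8, MM 0.6; overall mean 0.567), the noncentrality is 80 x (0.0711 + 0.0544 + 0.0011) = 10.13. Three-arm ANOVA power is then 81.6%, so the statement reproduces. Eighty per arm is taken as the ceiling for Aim 2, because D6j makes the EEG optional.

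**Assumptions not in the documents.** EEG numbers of 50, 60 or 80 per arm; two-sided 0.05 per test; EEG bands standardised and uncorrelated; residual SD 1; slopes of 0.3 or 0.4. For scale, the pilot EEG figure in section C calls associations above .30 moderate. Pain change is taken as pre minus post, as D6x defines it for Hypothesis 1.

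**Set-up.** Each arm's slope estimate has standard error 1/sqrt(n). The model has 12 parameters (3 arms x [intercept + 3 bands]), so residual df = 3n - 12. The theta condition is: 2-df F test significant, and HYP estimate the highest of the three.

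**False support for theta: slopes HYP 0, MM 0, ED -0.4.**

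- Noncentrality = n x sum of squared deviations of the slopes = n x 0.4² x 2/3. At n = 60 this is 6.4.
- The critical value of F(2, 168) is 3.05, and the F test is significant 60.5% of the time.
- HYP and MM have the same true slope and ED is almost never highest, so HYP is highest in about half of these: 60.5% / 2 = 30.3%.
- At 50 per arm, 52.2% / 2 = 26%. At 80, 74.1% / 2 = 37%.
- Simulation with 500,000 draws per case gives 26.0%, 30.3% and 37.1%.
- If the HYP estimate must also be positive, the figure at 60 per arm is 27%.

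**Effect of adding the slope test** (two-sided 0.05, stated direction), theta condition by simulation:

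| True slopes HYP / MM / ED | n per arm | Plan's rule | Plan's rule + HYP slope test |
|---|---|---|---|
| 0 / 0 / -0.4 | 60 | 30.3% | 2.4% |
| 0.4 / 0 / 0 | 60 | 60.2% | 59.3% |
| 0.3 / 0 / 0 | 60 | 36.4% | 34.4% |
| 0.4 / -0.4 / 0 | 60 | 96.7% | 86.2% |
| 0 / 0 / 0 | 60 | 1.6% | 0.8% |
| 0.3 / 0.3 / 0.3 | 60 | 1.7% | 1.7% |

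The first row cannot exceed 2.5% once the slope test is added, because that is the chance of a significant result in the stated direction when the HYP slope is zero. In the last row, a HYP slope test without the interaction would pass 64% of the time although there is no moderation. The interaction test therefore has to stay.

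**From one band to the full rule**, treating the bands as independent, 60 per arm:

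- ED theta slope only, nothing else: 0.30 x 0.017 x 0.017, below 0.01%.
- The same, with a true MM alpha slope of -0.4: 0.30 x 0.60 x 0.017 = 0.3%.
- ED slopes of 0.4 against the HYP prediction in both theta and gamma, plus the true MM alpha slope: 0.30 x 0.30 x 0.60 = 5.4%.

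A separate simulation at 80 per arm, with residual SD sqrt(0.91), HYP theta and gamma slopes of zero and a true MM alpha slope, gave these full-rule rates. With adverse slopes in one comparator arm: 3% at 0.30 and 19% at 0.50. With adverse slopes in both: 12% and 78%. With no EEG effect in any arm, each band passed about 1.7% of the time and all three together about 0%.

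**The case against.** The strongest reply is that the planned test fits the aim. Aim 2 asks about moderation relative to ED, and Treatment x EEG is the standard test of that. If ED has a theta slope and HYP has none, theta really does modify the HYP-ED difference, so the interaction is not spurious. This stands, and it is why the interactions should be kept. It does not rescue the further statement in Hypothesis 2 that pain reduction within HYP goes with theta.

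Second, false support needs a comparator slope that nothing in the documents predicts. Hypothesis 2 expects none in ED, and D6n describes ED as designed not to reduce pain. An analyst who looked at the fitted model would also see a HYP slope near zero. This limits how likely the problem is, but the written rule does not require that look.

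Third, a reader might take 30% as the chance that Aim 2 is wrongly declared supported. It is not: D6x requires all three bands.

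Fourth, a reader might infer that the rule is simply less powerful than a direct test. That depends on the pattern of slopes. At HYP 0.4 with the other arms at zero and 60 per arm, requiring the HYP slope and a 1-df contrast with the mean of the other arms gives about 70% against 60%. At HYP 0.4, MM -0.4, ED 0, it gives 86% against 97%. At 80 per arm and slope 0.30, the plan's rule (49%) is no weaker than a HYP-versus-ED contrast (48%), the comparison that the aim names.

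Finally, D6x draws no conclusion from non-significance in ED. That wording appears only in the hypothesis.

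**Conclusion.** The point holds per band. The rule in D6x can credit a named arm with an EEG association it does not have, if a comparator arm has a slope in the other direction. For theta with an ED slope of -0.4, this happens about 30% of the time at 60 per arm (26% at 50, 37% at 80). The size rests on assumed slopes, EEG numbers and a 0.05 level; the mechanism does not.

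The documents do not support a claim that Aim 2 as a whole carries that error rate. The full rule approaches such rates only with large adverse comparator slopes in both theta and gamma together with a real MM alpha effect. Nor do they support a general claim that the rule lacks power, or that an interaction test is the wrong tool. Hypothesis 2 is labelled secondary and Aim 1 is unaffected, so this is a tightening of the decision rule for a secondary hypothesis.

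**What to change.** In D6x, keep the regression and the three Treatment x EEG interaction tests. Add to the support rule that the slope in the named arm must differ from zero in the stated direction: HYP theta above zero, HYP left frontal gamma below zero, MM alpha below zero. State the significance level, and confirm that pain change is pre minus post for this model too. Report the ED slopes with 95% confidence intervals, and do not read non-significance as no association.

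The data and the model stay the same, and only SAP wording changes. At 60 per arm the power cost per band under the hypothesised pattern is about 1 point at slope 0.4 (60% to 59%) and 2 points at 0.3 (36% to 34%). It is larger if MM has an opposite slope (97% to 86% at +0.4 and -0.4). Replacing the 2-df test with a 1-df contrast is optional. If the sponsor wants one, the comparator should be chosen in advance with the aim's reference to ED in mind.

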Research staff will collect the following information from participants: (1) contact information; (2) preferred telephone number to reach an individual if they have more than one line; (3) permission to leave message on mobile/landline phones; (4) permission to send a text message and, if yes, cell phone carrier; (5) best times/days to reach participant; and (6) names and contact information of people staff are allowed to contact if participant is lost to follow-up or otherwise cannot be contacted (i.e. collateral contacts). The purpose of this is to maximize the likelihood of reaching a participant to complete the study procedures. Furthermore, asking permission to leave a voicemail on at a specified contact number ensures a greater level of privacy for the participant.

The information may be completed following enrollment either in person or over the telephone at a later time if more convenient for the participant.

D6i. Preparation for Brain Wave Activity (Electroencephalogram or EEG) Assessment

Research staff may ensure that the EEG net (device worn on the head that holds the EEG electrodes) will fit a participant's head prior to the EEG assessment. Research staff will cut a piece of string that is about 70 cm long, make two marks 62 cm apart, leaving a little on either end to hold on to. Research staff will wrap the string around participants' head in a circular loop that includes the following landmarks: 1) the point between the eyebrows above the nose (the glabella); 2) the point farthest back on the back of the head (the occipital protuberance); and 3) the sides of the head even with the tops of the ears. If the head circumference is greater than 62 cm, the staff member will inform the participant that the EEG equipment would not accommodate them and therefore they would not be able to participate in this study procedure.

Time permitting, research staff will send a letter to each participant that provides simple instructions to ensure quality data is collected from the participant during the assessment, e.g. requesting the participant clean his/her hair the day of the assessment, not wear jewelry, refrain from as needed medications, etc.

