Participants will report the skills s/he used during this assessment portion, as well as general experience during this portion. Participants will be compensated \$100 for completion of the brain wave activity assessment via a check written from the Seattle Institute for Biomedical and

Clinical Research (SIBCR). The check will be sent via USPS mail and accompanied by a payment cover letter.

Participants may still participate in the study if they decline to participate in the EEG assessments. The EEG assessment is optional.

D6k. Assessment: Pre-Treatment and General Overview

Subjective reports of pain intensity vary over time, and to most accurately measure pain intensity (our primary outcome), it is most valid to assess multiple times and take an average. Hence, we have developed a method of assessment that will seek to obtain up to four telephone assessments over a period of one week or 7 days. In addition, research staff will seek to administer these assessments ideally with a minimum of 24 hours between each assessment. Given scheduling conflicts, research staff may collect each assessment no less than 22 hours between each assessment if necessary.

During *each* telephone contact, research staff will ask participants, at minimum, to rate their current, average, worst and least pain intensity over the past 24 hours, as well as their average pain intensity over the past week.

In addition, if possible, research staff will ask the participant to rate their current, average, worst and least pain intensity over the past week during the final telephone contact. These assessments will be referred to as “short assessments.” The primary outcome will be an average of all of the 24-hour ratings (range=1-4 ratings) of average pain intensity obtained over a period of one week during each assessment period.

In addition, sometime during this assessment period researchers will ask questions regarding pain interference, depression, anxiety, sleep disturbance, post-traumatic stress disorder (PTSD) symptoms, medication use, medical services utilization, thoughts about pain and treatment motivation. This latter set of questions will only be asked once during the assessment period, and will be referred to as “the long assessment.”

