The assessment period described above will be completed prior to initiating treatment, and then after completion of treatment sessions #2, 4 and 6 and 8 (i.e. post-treatment), and 3 and 6 months following the end of treatment for a total of seven times. These assessment periods that occur following the start of treatment will also include questions about group climate, therapeutic alliance with the group clinician, treatment satisfaction, feedback about the treatment modality, and overall improvement since the participant began the pain program. The open-ended questions regarding treatment satisfaction and feedback on treatment modality will be collected by an unblinded staff member. Group Comfort Questions will be administered by an unblinded staff member at any time after session 8 (final group session). This assessment is optional. The window is from post-treatment until the participant is disenrolled.

Staff will send via USPS mail a reminder letter prior to the 3- and 6-month assessment periods.

As mentioned above, during the consent process research staff will provide participants with a response key to help answer questions asked during the telephone assessment periods. Participants may request research staff send another response key to them if they lose the key during study participation. Research staff will send the response key along with a cover letter via USPS mail.

Participants will be compensated \$25 for the completion of each assessment period via a check written from the Seattle Institute for Biomedical and Clinical Research (SIBCR). The check will be sent via USPS mail and accompanied by a payment cover letter.

The pre-treatment assessment period may take place up to four weeks prior to the start of the treatment groups for that particular cohort.

D6I. Randomization

Enrolled participants who complete the required baseline components (cognitive assessment, hypnotic and relaxation exercise, baseline data form, and pre-treatment assessment period) will be randomized in stratified blocks to ensure that participants with each sex/gender and pain type (neuropathic, non-neuropathic, mixed or undetermined) have an equal chance of being randomized to one of the 3 conditions. Stratification will assure that the treatment groups are balanced regarding each stratification variable, so that the estimated effect of the treatment is not biased due to differences in distribution of sex/gender or type of pain.

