The goal of mediation analyses is to examine whether group assignment (determined by randomization at baseline) impacts the change in pain intensity (primary outcome) from baseline to post-treatment through indirect effects on the hypothesized mediators (measured midway

between baseline and post-treatment). Our potential mediators have been identified a priori and are shown in the table of measures (Table 4).

To evaluate the association between intervention type, potential mediating factors, and change in pain intensity, we will first run models with individual mediators to get unadjusted estimates and to estimate the degree of confounding in subsequent multivariate models. Per Hayes & Rockwood's 2017 recommendations, we will test multiple mediators in the same model, to more accurately reflect our theoretical understanding of parallel biological and psychological mediating processes, and to facilitate comparison of the size of indirect effects through different mediators. Mediators to be included in the model include change in EEG composite scores for theta, alpha, beta, and gamma bandwidths, pain acceptance, catastrophizing, mindfulness, therapeutic alliance, and skill practice. Also per the recommendations of Hayes and Rockwood (2017), we will compute bootstrap confidence intervals for the indirect effects. All mediation analyses will be done using PROCESS, a free downloadable add-on available for SPSS and SAS (the analysis packages we will use for the study's data analysis). PROCESS includes the computational code to generate a primary estimate for the mediation model which represents the indirect, or mediated effect, and allows for inclusion of moderator variables.

Our study is longitudinal and, in addition to posttreatment assessments, we have collected data at 3- and 6-months post-treatment on outcomes and all other variables (mediators and moderators). While the approach used in the PROCESS software can be somewhat adapted for longitudinal analysis, the most appropriate analysis would be longitudinal structural equations models, particularly latent growth models (e.g., Goldsmith et al. 2018). These models require specialized software such as AMOS or LISREL and are beyond the scope of our exploratory aims. If we are able to access such statistical resources in the future, however, we would like to leverage this dataset for these exploratory purposes.

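### Exploratory mediation: the joint model mixes optional EEG change with mediators scheduled for everyone, so, unless EEG is imputed, it shrinks to people with two EEGs and the confounding check compares different samples

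*Combined protocol and SAP*

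**What the plan says.** D6x, Mediation analyses, sets out two steps. The first is "we will first run models with individual mediators to get unadjusted estimates and to estimate the degree of confounding in subsequent multivariate models". In the second, "we will test multiple mediators in the same model, to more accurately reflect our theoretical understanding of parallel biological and psychological mediating processes", and the sizes of the indirect effects through different mediators are then compared. The content of the joint model is given as "Mediators to be included in the model include change in EEG composite scores for theta, alpha, beta, and gamma bandwidths, pain acceptance, catastrophizing", followed by mindfulness, therapeutic alliance and skill practice: nine mediators, four of them EEG change scores.

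On EEG, D6j says: "Participants may still participate in the study if they decline to participate in the EEG assessments. The EEG assessment is optional". D6i adds a physical limit: "If the head circumference is greater than 62 cm, the staff member will inform the participant that the EEG equipment would not accommodate them". D6l lists what is needed before randomisation, "Enrolled participants who complete the required baseline components (cognitive assessment, hypnotic and relaxation exercise, baseline data form, and pre-treatment assessment period", and EEG is not on that list. EEG is recorded once before and once after treatment, at a separate university site.

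Table 5 schedules the psychological mediators in the main telephone assessments and does not mark them optional. Practice is also collected on class forms. The missing-data text, in D6x and again in D6y, is written for missing outcome data. It gives no rule for a missing mediator, and no analysis set is named for the single-mediator or the joint models.

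**The concern.** A regression row needs a value for every term in the model. With EEG change as a term and no rule for filling it in, a participant without both EEGs leaves the joint model and takes their psychological and practice data along. Two things are then at stake.

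The first is precision. Mediators that could have been studied in nearly the whole sample would be studied together only in the EEG subset, and the joint model is the one meant for comparing pathways.

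The second is interpretation. The single-mediator models serve "to estimate the degree of confounding in subsequent multivariate models". If they use everyone and the joint model uses a subset, a difference between them reflects the added adjustment and the change of people at once. Attendance at the second EEG also comes after randomisation, so the subset need not keep the balance that randomisation gave.

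**Working it through.** **Baseline n.** D6z plans 80 completers per arm, 240 in total, for at least 80% power on the primary outcome. A three-group ANOVA with the least favourable means (0.3, 0.8, 0.6), SD 1 and alpha 0.05 has sum of squared deviations 0.1267 and noncentrality 80 × 0.1267 = 10.13, which gives power 0.816; 78 per arm suffice for 80%. Enrolment of 240/(1 − 0.30) = 343 also matches the figure before it was raised to 355. The stated size reproduces, so 240 is the starting point.

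**Precision.** Let p be the share of the 240 with two usable EEGs. The documents give no p, so it is an assumed range.
- Joint-model n = 240 × p.
- Standard-error factor for a non-EEG mediator = 1/√p.
- Smallest partial correlation detectable with 80% power, two-sided 0.05, 11 predictors (two arm terms, nine mediators) = tanh[(1.96 + 0.84)/√(n − 13)].

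| p (assumed) | n | SE factor | Detectable partial r |
|---|---|---|---|
| 100% | 240 | 1.00 | 0.184 |
| 90% | 216 | 1.05 | 0.194 |
| 75% | 180 | 1.15 | 0.213 |
| 60% | 144 | 1.29 | 0.240 |
| 50% | 120 | 1.41 | 0.264 |
| 40% | 96 | 1.58 | 0.298 |

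**Confounding check.** A simulation (N = 240, 3,000 runs per setting) used one psychological mediator with true coefficient −0.30 and one EEG change score that, by construction, is not a confounder: it is unrelated to the mediator and has no effect on the outcome. The joint estimate in the subset was compared with the single-mediator estimate, first from all 240 and then from the same subset.

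| p (assumed) | Joint − full-sample single, random uptake: mean (SD) | Joint − full-sample single, uptake related to an effect modifier: mean (SD) | Joint − single in the same people, either uptake: mean (SD) |
|---|---|---|---|
| 90% | 0.000 (0.022) | 0.013 (0.024) | 0.000 (0.005) |
| 75% | 0.000 (0.040) | 0.030 (0.041) | 0.000 (0.006) |
| 50% | 0.000 (0.065) | 0.063 (0.071) | 0.000 (0.009) |

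The random-uptake SDs agree with a hand check. With unit residual SD and unit mediator SD, the SD of the difference is about (1/√240) × √(1/p − 1), or 0.022, 0.037 and 0.065.

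In the middle column, uptake and the mediator's effect both depend on one unobserved trait (log-odds slope 1.0 for uptake; change in the mediator effect of 0.15 per SD). Those strengths are assumptions. With no confounding present, comparing different people adds noise in every case, and a mean shift only under that selection. Using the same people removes the shift and most of the noise.

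**The case against.** The plan nowhere says that rows without EEG are dropped. That is inferred from the absence of a mediator rule. If EEG change were imputed, the sample would be restored. This stands as a limit, but imputation would have to be written down, and the multiple imputation in the plan is for outcomes.

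Uptake may be high. D6a describes research participants as doing all assessments including EEG, Table 1 places randomisation after all baseline procedures, and D6o pays $100 per EEG. The explicit optional status in D6j and the list in D6l are more specific, yet nothing in the documents supports a low uptake, and at 90% the precision loss is small.

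The comparator of 240 is idealised. D5 counts as a completer anyone with at least one assessment after randomisation, so some will lack mediator or post-treatment pain data. To the extent that they also lack a second EEG, the real loss is smaller than 1/√p.

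A reader might infer that the psychological mediators are tested only in people with two EEGs. The documents do not support that: nothing stops the single-mediator models from using everyone with the measure. A reader might also infer that the confounding check will be biased. That needs uptake to be related to something that alters the mediator's effect, for which the documents give no evidence. D6x sets no decision rule on the comparison either.

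Finally, these analyses are declared exploratory, and the plan promises to report all results and the number of analyses run. That lowers the priority. It does not make the single and joint estimates comparable.

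**Conclusion.** The point holds for the joint model and for the single-versus-joint comparison. It rests on EEG change not being imputed. On that footing, the non-EEG mediators lose precision by a factor of about 1.05 at 90%, 1.15 at 75% and 1.41 at 50% with two EEGs. These shares are assumptions, and the factors are best read as upper figures, given that people without a second EEG will often lack other data too. The comparison of single and joint estimates carries added noise from the change of sample. A systematic shift is possible but conditional on selection. The tests of Hypotheses 1 and 2 do not use this model and are unaffected by this point. It is a low-priority but inexpensive improvement to the mechanism analyses.

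**What to change.** In D6x, Mediation analyses:

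1. Add a joint model of pain acceptance, catastrophizing, mindfulness, therapeutic alliance and skill practice on all randomised participants with those measures.
2. Keep the combined EEG-plus-psychological model in participants with both EEGs, for comparing biological and psychological pathways.
3. Rerun the single-mediator models in that same subset, and make any single-versus-joint comparison only between models fitted to the same people.
4. Report n for each model, and state how missing EEG is handled, including whether EEG change is imputed.

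The cost is wording plus one extra joint model and five to nine single-mediator reruns: five if the EEG single-mediator models already use the common set, nine if all are refitted to it. No new data are needed. The downside is that the full-sample psychological model is not adjusted for EEG change, so pathways are compared directly only within the EEG subset.
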